7.3.2.1 Demographics

- Age (descriptive statistics)
- Age categories (<65, \geq 65 and <75, \geq 75)
- Gender (male, female)

- Race (White, Black/African American, American Indian/Alaska Native, Native Hawaiian/Other Pacific Islander, Asian Indian, Chinese, Japanese, Asian Other, Other)
- Weight (descriptive statistics)
- ECOG Performance Status (0, 1, > 1)
- Region (US/Canada/Europe, Asia, Asia excluding Japan, Japan)

7.3.2.2 HCC Etiology

HCC etiology is a description of disease subtype at baseline and includes HBV-infected, HCV-infected, uninfected, and HBV-HCV coinfection. HCC etiology is derived based on risk factors as collected on CRF, and described below:

- Etiology is HBV-infected if HBV is a risk factor, and HCV is not included as a risk factor
- Etiology is HCV-infected if HCV is a risk factor, and HBV is not included as a risk factor
- Etiology is HBV-HCV coinfection if both HBV and HCV are included as risk factors
- Etiology is uninfected if neither HBV nor HCV is considered as a risk factor

Upon review of data, there are a few subjects with both HBV and HCV boxes checked in the risk factor CRF page. Clinical review suggested that these subjects might be similar to HCV subjects. Therefore, these subjects are grouped together with HCV subjects for all outputs of the clinical study report.

7.3.2.3 HCC Disease Characteristics

The following disease characteristics will be summarized. All available data will be listed.

- HCC Risk Factors
- Vascular invasion (Yes/No)
- Extrahepatic spread (Yes/No)
- Disease etiology (Uninfected/HCV-infected/HBV-infected/HBV-HCV coinfection)
- Child-Pugh Score (Class and Score)
- Liver Nodules (Yes/No)
- BCLC (Barcelona clinic liver cancer) stage
- AFP (descriptive statistics)
- AFP Category (≥ 200 , < 200 , ≥ 400 , < 400)
- Time from initial diagnosis of HCC to randomization

7.3.3 Medical History and Pre-treatment Events

General medical history will be listed by subject. HCC or prior treatment-related pre-treatment events will be summarized by worst CTC grade, system organ class and preferred term.

7.3.4 Prior Anti-Cancer Therapies

Prior anti-cancer therapies include the following therapies and will be summarized.

- Prior systemic cancer therapy (Yes/No)
- Prior surgery therapy (Yes/No)
- Prior radiotherapy (Yes/No)
- Prior non-systemic treatment related to HCC local only (Yes/No)

7.3.5 Baseline Examinations

Subjects with abnormal baseline physical examination will be tabulated by examination criteria and by treatment group.

7.3.6 Discrepancies Between IVRS and CRF Stratification Factors

A summary table (cross-tabulation) by treatment group as randomized for stratification factor will be provided to show any discrepancies between what was reported through IVRS and CRF data.

7.4 Extent of Exposure

Analyses in this section will be performed in all treated subjects by treatment group as treated (as defined in [Section 6.3](#)). Listings will include all available exposure data.

Table 7.4-1 summarizes the key parameters used to calculate dosing data.

Table 7.4-1: Administration of study therapy: definition of parameters

	Nivolumab	Sorafenib
Dosing schedule per protocol	240mg every 2 weeks	400mg BID
Dose	Dose (mg) is defined as Total Dose administered. Dose administered in mg at each dosing date are collected on the CRF.	Dose (mg) is defined as Total Dose administered. Dose administered in mg at each dosing date are collected on the CRF.
Cumulative Dose	Cum dose (mg) is sum of the doses (mg) administered to a subject during the treatment period.	Cum dose (mg) is sum of the doses (mg) administered to a subject during the treatment period.
Relative dose intensity (%)	$\text{Cum dose (mg)} / [(\text{Last dose date} - \text{Start dose date} + 14) \times 240 / 14] \times 100$	$\text{Cum dose (mg)} / [(\text{Last dose date} - \text{Start dose date} + 1) \times 800] \times 100$
Duration of treatment	Last dose date - Start dose date +1	Last dose date - Start dose date +1

7.4.1 Administration of Study Therapy

The following parameters will be summarized by treatment group (descriptive statistics):

- Relative dose intensity (%) using the following categories: < 50%; 50 - < 70%; 70 - < 90%; 90 - < 110%; ≥ 110%.

- Number of doses received
- Cumulative dose
- Duration of treatment: duration of treatment will be presented using a KM curve whereby the last dose date will be the event date for subjects who discontinued study therapy and last dose date will be the censoring date for subjects who are still on study therapy. Median duration of treatment and associated 95% CI will be provided.
- A by-subject listing of dosing of study medication (record of study medication and dose change) and a listing of batch number will be also provided. Infusion details will also be provided for nivolumab.
- Time from randomization to first dose of nivolumab or sorafenib (0 to 3 days, 4-5 days, 6-7 days, 8-14 days, 15-21 days, 22-28 days, > 28 days).

7.4.2 *Modification of Study Therapy*

7.4.2.1 *Dose delay for nivolumab*

A dose given more than 3 days after the intended dose date will be considered a delay. Treatment may be delayed for up to a maximum of 6 weeks (42 days) from the last dose.

Length of delay is defined as duration of interval from prior dose in days minus 14 days. Dose delays will be divided into following categories: 4 - 7 days, 8 - 14 days, 15 - 42 days, 43 - 84 days, and \geq 85 days. Dose delay events and reason for dose delay will be retrieved from CRF dosing pages.

The following parameters will be summarized for nivolumab treatment group:

- Number of subjects with at least one dose delayed, number of dose delayed per subject, length of delay, and reason for dose delay

7.4.2.2 *Dose delay for sorafenib*

Dose delay will occur if the subject did not receive any dose during at least one day for a different reason than “Dosing Error”, provided that treatment was resumed afterwards.

Length of delay is defined as duration of interval from prior dose in days. Dose delays will be divided into following categories: \leq 1 day, 2 - 3 days, 4 - 7 days, 8 - 14 days, 15 - 42 days, 43 - 84 days, and \geq 85 days. Dose delay events and reason for dose delay will be retrieved from CRF dosing pages.

The following parameters will be summarized for sorafenib treatment group:

- Number of subjects with at least one dose delayed, number of dose delayed per subject, length of delay, and reason for dose delay

7.4.2.3 *Dose modifications for nivolumab*

No dose modifications for nivolumab are allowed.

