#### **4.5.3.3 Treatment Interruption or Discontinuation Criteria for Sorafenib**

The decision to interrupt or discontinue sorafenib should follow local standards of care as guided by the locally approved product label or applicable SmPC.

For any dose interruptions, re-initiation of study drugs therapy may be delayed for a maximum of 30 days to allow recovery from any adverse event. In exceptional cases where subjects are responding, re-initiation of therapy after missing > 30 consecutive days of treatment may be done on a case by case basis after confirmation with the BMS medical monitor.

Tumor assessments for all subjects should continue as per protocol even if dosing is delayed.

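### SAP 7.4.2.2 measures a sorafenib dose delay from the prior dose, so each gap comes out one day too long and the ≤ 1 day row cannot fill

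*SAP*

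**What the plan says.** For sorafenib, SAP 7.4.2.2 defines the event by days without drug: "Dose delay will occur if the subject did not receive any dose during at least one day for a different reason than" a dosing error, provided that treatment was later resumed. The length is defined separately: "Length of delay is defined as duration of interval from prior dose in days. Dose delays will be divided into following categories". The rows open at ≤ 1 day and run "1 day, 2 - 3 days, 4 - 7 days, 8 - 14 days, 15 - 42 days", followed by 43–84 and ≥ 85 days.

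For nivolumab, SAP 7.4.2.1 counts a delay when a dose is given more than 3 days late. Its length rule takes off the dosing interval: "Length of delay is defined as duration of interval from prior dose in days minus 14 days". The rows start at 4–7 days and share the 15–42, 43–84 and ≥ 85 day bands with sorafenib.

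SAP Table 7.4-1 fixes the time resolution of the data: "Dose administered in mg at each dosing date are collected on the CRF".

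The documents also state limits. For nivolumab, SAP 7.4.2.1 says "Treatment may be delayed for up to a maximum of 6 weeks (42 days) from the last dose". For sorafenib, Protocol 4.5.3.3 says "re-initiation of study drugs therapy may be delayed for a maximum of 30 days to allow recovery from any adverse event". Protocol 4.5.1.5 and 4.5.3.3 each provide exceptions to these limits.

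**The concern.** The sorafenib event and the sorafenib length are counted on different scales. The event is at least one day with no dose. The length is the whole interval back to the last dose, which on a once-or-more-daily schedule includes a day even when nothing was missed. A table whose first row is ≤ 1 day only makes sense if length means days without drug, but the text does not say that.

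What is at stake is modest. A programmer who follows the text produces a table with a structurally empty first row, single-day gaps reported as 2–3 days, and any mean or median length one day too high. A reader could take the empty row to mean that no patient had a brief interruption.

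**Working it through.** **Inputs**

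- Sorafenib event: m ≥ 1 days with no dose, then resumption (SAP 7.4.2.2).
- Sorafenib length: interval from prior dose, nothing subtracted (SAP 7.4.2.2).
- Sorafenib rows: ≤ 1, 2–3, 4–7, 8–14, 15–42, 43–84, ≥ 85 days (SAP 7.4.2.2).
- Dosing recorded by date (SAP Table 7.4-1).
- Nivolumab: delay if more than 3 days late; length = interval − 14; first row 4–7 days (SAP 7.4.2.1).

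**Step 1. Reproduce the SAP's own nivolumab figure.** The shortest interval that is more than 3 days late is 14 + 4 = 18 days. Length = 18 − 14 = 4, which is the lower bound of the first row. The nivolumab rule is consistent with its table, and it works on plain date differences.

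**Step 2. Apply the same day count to sorafenib.** If the last dose is on day d and m days are missed, dosing resumes on day d + m + 1. Length = (d + m + 1) − d = m + 1. The smallest case is m = 1: last dose day 10, restart day 12, length 12 − 10 = 2. Every gap is one day too long, and no delay can have length ≤ 1.

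**Step 3. Map missed days to rows.**

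| Row | Missed days that land there as written (m + 1) | Missed days that land there if length = m |
|---|---|---|
| ≤ 1 | none | 1 |
| 2–3 | 1–2 | 2–3 |
| 4–7 | 3–6 | 4–7 |
| 8–14 | 7–13 | 8–14 |
| 15–42 | 14–41 | 15–42 |
| 43–84 | 42–83 | 43–84 |
| ≥ 85 | 84 or more | 85 or more |

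Gaps of exactly 1, 3, 7, 14, 42 and 84 missed days change row. Other gaps keep their row but carry a length one day too high.

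**Step 4. Would clock times rescue the first row?** No. A full calendar day with no dose puts more than 24 hours between doses. An evening dose at 20:00 and a restart at 08:00 two days later are 36 hours apart, or 1.5 days.

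**Step 5. What the SAP's own logic implies.** In the relative dose intensity formulas of Table 7.4-1, the last dose is credited with 14 days for nivolumab and 1 day for sorafenib. The sorafenib counterpart of subtracting 14 is subtracting 1, which gives length = m and lets every row fill.

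**Step 6. Where the stated limits fall.** For nivolumab, 42 days from the last dose is 42 − 14 = 28 net days. The 15–42 row covers intervals of 15 + 14 = 29 to 42 + 14 = 56 days, so it holds net lengths 15–28 (within the stated limit) and 29–42 (beyond it). For sorafenib, 30 and 31 missed days have lengths 31 and 32 as written, or 30 and 31 after correction. Either way both sit in the same 15–42 row.

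**The case against.** The best defence is that the wording is loose rather than wrong. The event is defined by days without drug, the rows open at ≤ 1 day, and delay events are to be taken from CRF dosing pages that are not in the documents. A programmer may well count missed days, and then the row fills. That is a fair account of the likely intention, but the stated rule says otherwise and the plan should not depend on its being ignored. It is also fair that only six exact gap lengths change row.

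A reader might go further in four ways that the documents do not support:

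- **That lengths are wrong in both arms.** They are not; the nivolumab rule reproduces its own first row (18 − 14 = 4).
- **That the overstatement is two days**, from the end-minus-start-plus-1 convention in SAP 8.2. That convention does not fit the delay arithmetic. A nivolumab dose exactly 3 days late (17-day interval) is not a delay, yet would get 17 + 1 − 14 = 4 and enter the first row. The examples in SAP 8.2 are also not dosing intervals.
- **That the 15–42 day row hides breaches of the protocol limits.** Both arms allow longer delays in stated circumstances, so passing a limit is not in itself a breach. The sorafenib limit concerns recovery from adverse events, while the SAP delay covers almost any reason. By-subject dosing listings are planned, and rows from 43 days up already lie beyond both limits. Delay limits are not among the programmable deviations in SAP 7.2.2, but nothing says these descriptive bands are meant to test compliance.
- **That the between-arm comparison is biased.** The SAP summarises each arm's delays separately, with different event definitions and different rows.

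**Conclusion.** The point holds for the sorafenib length rule only. As written, each sorafenib delay is overstated by one day, the ≤ 1 day row is empty by construction, and gaps of exactly 1, 3, 7, 14, 42 or 84 missed days are tabulated one row too high. This rests on taking the interval from prior dose as a date difference, which is how the nivolumab rule behaves and how the dosing data are recorded. The documents give no distribution of gap lengths, so the number of patients placed in a wrong row cannot be stated.

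The consequence is limited to a descriptive exposure table. Nivolumab delay lengths, relative dose intensity, OS, ORR, PFS, alpha and power are unaffected. The position of the 15–42 day row relative to the stated limits is a matter of presentation, not an error, and no view is taken here on the limits themselves.

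**What to change.** In SAP 7.4.2.2, define sorafenib length of delay as date of resumed dose − date of last dose − 1, that is, the number of days without a dose. The rows can stay as they are.

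Optionally, split the 15–42 day row for display at the limits the documents already state: 15–28 and 29–42 net days for nivolumab, 15–30 and 31–42 days for sorafenib. The longer bands should not be labelled as breaches.

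The cost is one SAP line, plus a small change to the table shell if the split is adopted. The dosing dates are already collected. Since SAP 7.10 records the primary database lock as 5 June 2019, any table already produced should be checked for which count the program used, and rerun or footnoted if it used the interval from the prior dose.

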7.4.2.4 Dose modifications for sorafenib

When dose reduction is necessary during the treatment of HCC, the sorafenib dose should initially be reduced to two tablets of 200 mg sorafenib once daily. For further dose reductions, refer to the sorafenib SmPC or locally approved product label for additional details.

The following parameters will be summarized for sorafenib treatment group:

- Number of subjects receiving sorafenib with at least one dose reduction and reasons for dose reduction.

7.4.2.5 Infusion interruptions and rate changes for nivolumab

The following parameters will be summarized for nivolumab:

- Number of subjects with at least one dose infusion interruption, number of infusion interruptions per subject, and the reason for interruption.
- Number of subjects with at least one IV infusion rate reduction, number of IV infusion rate reduction per subject, and the reason for reduction.

7.4.3 Concomitant Medications

Concomitant medications, defined as medications other than study medications which are taken at any time on-treatment (i.e. on or after the first day of study therapy and within 100 days following the last dose of study therapy), will be coded using the WHO Drug Dictionary.

The following summary tables will be provided:

- Concomitant medications (subjects with any concomitant medication, subjects by medication class and generic term).

A by-subject listing will accompany the table.

7.5 Efficacy

Unless otherwise specified, all analyses are based on treatment group as randomized.

7.5.1 Primary Efficacy Endpoint OS Analyses

7.5.1.1 Primary Analysis

The distribution of OS will be compared in two randomized arms via a two-sided α stratified log-rank test where α will be determined as per [Section 7.5.4.2](#).

7.5.1.2 Secondary Analyses

A stratified Cox proportional hazards regression model will be used to estimate hazard ratio (see [Section 7.1](#)) between treatment groups along with the $100(1-\alpha)\%$ CI where α will be determined as per [Section 7.5.4.2](#).

For descriptive purpose, the 95% CI for the estimated hazard ratio in [Section 7.5.1.1](#) will be provided.

The OS curves for each treatment group will be estimated using the KM product-limit method. Median OS and the corresponding two-sided 95% confidence intervals using the log-log transformation will be computed.

Survival rates at 12, 18, 24, 36, 48 months and 5 years will be estimated using KM estimates on the OS curve for each randomized arm. Minimum follow-up (see its definition in [Section 7.5.1.5](#)) must be longer than a time period to generate a rate. Associated two-sided 95% CIs will be calculated.

The status of subjects who are censored in the OS KM analysis will be tabulated for each treatment group using following categories:

- On-study: (on treatment and not progressed, on-treatment progressed, in follow-up)
- Off-study: (lost to follow-up, withdraw consent, other)

7.5.1.3 Sensitivity Analyses

OS will be compared between treatment groups using a two-sided α (the same as in the primary analysis) unstratified log-rank test.

OS will also be compared between treatment groups using the strata as determined at baseline (CRF source) if the stratification variables at IVRS and at baseline disagree for at least 10% of the randomized subjects.

7.5.1.4 Consistency of Treatment Effect on OS in Subsets

To assess consistency of treatment effects in different subsets, a “forest” plot of the OS hazard ratio and 95% CI will be produced for the following variables, but not limited to:

- Geography (Asia vs Non-Asia)
- Region (US/Canada/Europe, Asia, Asia excluding Japan, Japan)
- Age categorization I ($< 65, \geq 65$)
- Age categorization II ($< 65, \geq 65 - < 75, \geq 75$)
- Age categorization III ($< 65, \geq 65 - < 75, \geq 75 - < 85, \geq 85$)
- Age categorization IV ($< 30, \geq 30 - < 45, \geq 45 - < 60, \geq 60$)
- Gender (Male vs. Female)
- Race (White, Black/African American, American Indian/Alaska Native, Native Hawaiian/Other Pacific Islander, Asian Indian, Chinese, Japanese, Asian Other, Other)
- ECOG (0, 1, > 1)
- Child-Pugh Score (5, 6, (7, 8, 9 or above))
- Child-Pugh Class (A, B, C)
- Etiology (HCV-infected, HBV-infected, uninfected, HBV-HCV coinfection) from CRF
- Vascular invasion and/or extrahepatic spread (present or absent) from CRF
- AFP categorization I at baseline (AFP > 200 ng/ml, and AFP ≥ 200 ng/ml)

- AFP categorization II at baseline (AFP < 400 ng/ml and AFP \geq 400 ng/ml)
- PD-L1 status at baseline (see [Section 4.3.3](#))
- BCLC category at baseline

If a subgroup category has less than 10 subjects in a treatment group, then HR will not be reported for that subgroup.

7.5.1.5 *Subject Follow-up*

The minimum follow-up will be reported. The minimum follow-up is defined as the time interval between the last patient's randomization date and the clinical cutoff date.

The extent of follow-up defined as the time between randomization date and last known date alive (for subjects who are alive) or death date (for subjects who died) will be summarized descriptively (median, min, max) for all randomized subjects.

The currentness of follow-up for survival, defined as the time between last OS contact (ie, last known date alive or death date) and data cutoff date (defined by last patient last visit date), will be summarized by treatment group. Subjects who died before data cutoff date or subjects whose last known date alive is on or after data cut-off date will have currentness of follow-up set to zero. The currentness of follow-up will be categorized into the following categories: 0 day, 1 day-3 months, 3-6 months, 6-9 months, 9-12 months and \geq 12 months.

7.5.1.6 *Subsequent Therapy*

Subsequent therapy will be summarized by treatment group and listed. The following information pertaining to subsequent therapies will be summarized:

- Systemic anti-cancer therapy by drug name
- Surgery
- Radiotherapy
- Non-systemic treatment for HCC (local only)

A by-subject listing of follow-up therapy will be produced for subjects who had any subsequent therapy.

7.5.2 *Secondary Efficacy Endpoint ORR Analyses*

Hierarchical testing of ORR will be performed upon demonstration of superiority in OS at OS interim or final analyses for all randomized subjects (see [Section 7.5.4.2](#)). P-values will not be presented for ORR if the endpoint OS whose null hypothesis could not be rejected. In this case, descriptive analysis and treatment difference estimations for ORR will still be presented.

Primary Analysis

ORR based on BICR assessment per RECIST 1.1 will be compared between two treatment groups using a two-sided Cochran-Mantel-Haenszel (CMH) test, stratified by the stratification factors. This comparison will only be tested if the OS comparison is positive.

Secondary Analyses

For descriptive purpose, the following statistics will be provided.

- An estimate of the differences in ORRs and corresponding 95% CI will be calculated.
- ORR along with its 95% exact CI using the Clopper-Pearson method will be computed for each treatment group.
- In addition, the stratified (source: IVRS) odds ratios (Mantel-Haenszel estimator) between the treatments will be provided along with the 95% CI.
- BOR will be summarized by response category.

Sensitivity Analyses

Similar analysis of ORR as in the secondary analyses will be performed for response evaluable subjects.

ORR might also be analyzed in some key subgroups based on patients' baseline characteristics.

7.5.3 Secondary Efficacy Endpoint PFS Analyses

PFS as secondary efficacy endpoint is defined in [Section 4.3.2](#). Hierarchical testing of PFS will be performed upon demonstration of superiority in OS and superiority in ORR at OS interim or final analyses for all randomized subjects (see [Section 7.5.4.2](#)). P-values will not be presented for PFS if the primary endpoint OS's null hypothesis could not be rejected or the secondary endpoint ORR's null hypothesis could not be rejected. In this case, descriptive analysis and treatment difference estimations for PFS will still be presented.

Primary Analysis

PFS will be compared between the two treatment groups via the stratified log-rank test. This comparison will only be tested if the OS comparison is positive and the ORR comparison is positive.

Secondary Analyses

A stratified Cox proportional hazards regression model will be used to estimate hazard ratio (see [Section 7.1](#)) between treatment groups along with the $100(1-\alpha)\%$ CI (adjusted for multiplicity, see [Section 7.5.4.2](#)).

For descriptive purpose, the 95% CI for the estimated hazard ratio will be provided.

The PFS curves for each treatment group will be estimated using the KM product-limit method. Median PFS and the corresponding two-sided 95% confidence intervals using the log-log transformation will be computed.

In each treatment group, the 6, 12, 18, 24, 36, 48 months and 5 year PFS rate along with 95% CI will be estimated from the Kaplan-Meier estimate. Minimum follow-up (see its definition in [Section 7.5.1.5](#)) must be longer than a time period to generate a rate. The associated two-sided 95% CI will also be calculated.

The source of progression (death vs progression) will be summarized by treatment group.

The status of subjects who are censored in the PFS Kaplan-Meier analysis will be tabulated for each treatment group using following categories:

- Never treated
- On-study (on treatment, in follow-up)
- Off-study (lost to follow-up, withdraw consent, other).
- Received subsequent anti-cancer therapy

Sensitivity Analyses

[figure not shown]
Sensitivity analyses of PFS will also be performed using the following modification of PFS primary definition.

PFS accounting for assessment on/after subsequent therapy It will be defined similarly to the primary definition except that events (progression or death) and tumor assessments that occurred on or after subsequent anticancer therapy will be taken into account (see censoring scheme in Table 7.5.3-1 and Figure 7.5.3-1).

Table 7.5.3-1: Censoring Scheme - PFS Sensitivity Analysis

Situation	Date of Progression or Censoring	Outcome
No baseline tumor assessment	Date of randomization	Censored
No on study tumor assessments and no death	Date of randomization	Censored
Documented progression per BICR assessment according to RECIST 1.1	Date of the first documented tumor progression	Progressed
No progression and no death	Date of last tumor assessment	Censored
Subsequent anti-cancer therapies started without a prior reported progression	Date of subsequent anti-cancer therapy not considered	None
Death without progression and without initiation of subsequent anti-cancer therapy	Date of death	Progressed
Death without progression after initiation of subsequent anti-cancer therapy	Date of death	Progressed

Figure 7.5.3-1: Graphical Display of PFS Definition for Sensitivity Analysis

The secondary endpoint of PFS might also be analyzed in some key subgroups based on patients' baseline characteristics.

7.5.4 *Interim Analyses and Multiple Comparison*

7.5.4.1 *Interim Analyses*

An independent statistician external to BMS will perform the interim analyses, and DMC will have access to periodic unblinded interim reports of efficacy and safety.

In addition to the formal planned interim analysis for OS, the DMC will conduct every 6 months review of safety. At each safety review, the DMC may have access to interim reports of safety and limited efficacy (such as KM curves of OS) to allow appropriate risk/benefit assessment. Details are included in the DMC charter.

The DMC will review the safety and efficacy data from the interim analysis and will determine if the study should continue with or without changes or if accrual should be stopped. Subject enrollment will continue while waiting for the DMC's decisions. More details of the interim analyses are discussed in the Data Monitoring Committee Charter.

7.5.4.2 *Stagewise Hierarchical Testing Procedure for Primary Endpoint OS and Secondary Endpoints ORR and PFS*

Let $i = 1, 2, 3$ denote index indicating primary endpoint OS and secondary endpoints ORR and PFS, respectively. Accordingly, H_1, H_2, H_3 denote two-sided null hypotheses of no effect in primary endpoint OS and secondary endpoints ORR and PFS, respectively. Let $t = 1, 2$ denote

index indicating interim and final analysis timings, respectively. Correspondingly, $p_{i,t}$ denote nominal p-value of testing H_i at the analysis time t , and the corresponding decision boundaries can be expressed as nominal significance levels $a_{i,t}^*$ such that H_i is rejected if $p_{i,t}$ is smaller than $a_{i,t}^*$ at time t .

To strongly control FWER at level 0.05 across three endpoints and repeated analyses at interim and final analyses, we adopted the stagewise hierarchical testing procedure³⁶ to test H_1 , H_2 , H_3 . Specifically, at the interim analysis time H_1 is tested with nominal significance level $a_{1,1}^*$ leading to the following two possibilities of rejecting H_1 :

[figure not shown]
- If $p_{1,1} < a_{1,1}^*$, H_1 will be rejected, the trial will stop and H_2 will be tested with nominal significance level $a_{2,1}^*$. If $p_{2,1} < a_{2,1}^*$, H_2 will be rejected and H_3 will be tested with nominal significance level $a_{3,1}^*$ with $p_{3,1} < a_{3,1}^*$ leading to the rejection of H_3 . If $p_{2,1} \geq a_{2,1}^*$, H_2 will not be rejected and H_3 will not be tested.
- If $p_{1,1} \geq a_{1,1}^*$, the trial continues to final analysis time and H_1 will be tested with nominal significance level $a_{1,2}^*$. If $p_{1,2} < a_{1,2}^*$, H_1 will be rejected and H_2 will be tested with nominal significance level $a_{2,2}^*$. If $p_{2,2} < a_{2,2}^*$, H_2 will be rejected and H_3 will be tested with nominal significance level $a_{3,2}^*$ with $p_{3,2} < a_{3,2}^*$ leading to the rejection of H_3 . If $p_{2,2} \geq a_{2,2}^*$, H_2 will not be rejected and H_3 will not be tested.

The nominal significance levels for OS $a_{1,1}^*$ and $a_{1,2}^*$ will be computed using EAST software based on a generalization of the Lan-DeMets error spending function approach using an O'Brien-Fleming stopping boundary given overall two-sided alpha = 0.05. The stopping boundary will depend on the actual number of OS events observed at the time of the interim analysis and the final analysis. However, if the interim analysis is performed exactly when 80% OS events are observed, then $a_{1,1}^* = 0.024$ will be used for the interim analysis and $a_{1,2}^* = 0.043$ will be used for the final analysis.

The nominal significance levels for ORR will be pre-specified as $a_{2,1}^* = 0.025$ and $a_{2,2}^* = 0.025$, as an equal Bonferroni splitting of the two-sided alpha = 0.05.

The nominal significance levels for PFS $a_{3,1}^*$ and $a_{3,2}^*$ will be computed using EAST software based on a generalization of the Lan-DeMets error spending function approach using an Pocock stopping boundary given overall two-sided alpha = 0.05. The stopping boundary will depend on the actual number of PFS events observed at the time of the interim analysis and the final analysis. 722 PFS events are expected at the final analysis time (of OS). 704 out of 722 or 97.5% PFS events are expected at the interim analysis time. If the interim analysis is performed exactly when 97.5% PFS events are observed, then $a_{3,1}^* = 0.049$ and $a_{3,2}^* = 0.031$ will be used.

